This proof-of-concept study will consist of a screening/randomization period (up to 4 weeks), a treatment period (from Day 1 to Week 44), and an observational period (from Week 44 up to Week 72). The total study length will thus be up to 76 weeks.

The study will evaluate the effects of RO7200220 in combination with the anti-VEGF inhibitor ranibizumab (Lucentis®) on visual function and retinal structure by assessing changes from baseline in best corrected visual acuity (BCVA; ETDRS letters) and anatomical outcomes (imaging assessments), respectively. The anti-VEGF inhibitor ranibizumab (Lucentis®) will be the active comparator. In addition, the safety, tolerability, pharmacokinetics, and pharmacodynamics of RO7200220 in combination with ranibizumab will be evaluated.

Participants will be carefully monitored for potential ocular adverse events (AEs) associated with the IVT injection procedure and for other potential ocular and systemic effects associated with the IVT administration of RO7200220 and ranibizumab, and will be managed appropriately.

TREATMENT GROUPS AND DURATION

The two groups of this study will be:

- Arm A: 1.0 mg RO7200220 IVT Q4W and ranibizumab 0.5 mg IVT Q4W
- Arm B: 0.5 mg ranibizumab IVT Q4W (active-control arm)

Participants will be randomized 1:1 to one of the study arms.

During the treatment period, the study drug will be administered to the participants on Day 1 and on every 4th week (Q4W), for a total of 12 injections.

A sham procedure will be administered to participants in the ranibizumab only arm at applicable visits to maintain masking between treatment arms.

^{*} All BCVA values are measured on the ETDRS chart at a starting distance of 4 meters.

The investigational medicinal products (IMP) are RO7200220 and 0.5 mg ranibizumab administered IVT.

LENGTH OF STUDY

The total study length will be up to 76 weeks, divided as follows:

Screening/randomization period: up to 4 weeks
 Treatment period: Day 1 to Week 44

Observational period: Week 44 up to Week 72.

END OF STUDY

A participant is considered to have completed the study if he/she has completed all phases of the study, including the EOS visit. The end of the study is defined as the date when the last participant, last observation (LPLO) occurs.

DATA MONITORING COMMITTEE:

A Roche Internal Monitoring Committee (IMC) will be responsible for the unmasked interim analysis of efficacy for operational/administrative/study related purposes and for safety data monitoring).

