- 6. Macular edema associated with DR defined as macular thickening by SD-OCT involving the center of the macula: CST of $\geq 325~\mu m$ with Spectralis® (Heidelberg Engineering, Heidelberg, Germany; where Spectralis® is not available, Cirrus or Topcon would also be acceptable with a CST threshold of $\geq 315~\mu m$) at screening. Note: CST is not part of the eligibility reconfirmation on Day 1.
- 7. Decreased visual acuity (VA) attributable primarily to DME, with BCVA letter score of 73 to 19 letters (both inclusive; 20/40 20/400 Snellen equivalent) on ETDRS-like charts at screening.
- 8. Clear ocular media and adequate pupillary dilation to allow acquisition of good quality retinal images to confirm diagnosis.

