6.3 MEASURES TO MINIMIZE BIAS: RANDOMIZATION AND MASKING

6.3.1 Method of Treatment Assignment and Masking

After written informed consent has been obtained, all participants will receive a screening number assigned through the interactive voice and web response system (IxRS).

A participant must meet all eligibility criteria (see Section 5.1 and Section 5.2) at the screening or Day 1 visit prior to randomization and first study treatment (see Section 8.9). As part of the screening process, FP, FFA, and SD-OCT will be transferred to the CRC, and the images will be evaluated to provide an objective, masked assessment of certain eligibility criteria.

After all participant eligibility requirements are confirmed on Day 1 visit, the site personnel will contact the IxRS for assignment of a participant identification number (a separate number from the screening number).

Participants will be randomized on the same day the study treatment is to be initiated (Day 1 visit).

Note: If a site has an unexpected issue (e.g., the IxRS is not able to assign the study kit), a participant's randomization and first study treatment may be administered within 2 business days of the Day 1 visit assessments, after consultation with the Medical Monitor. The following assessments will be repeated on the day of randomization and study treatment administration: urine pregnancy test (if applicable), slit lamp examination, indirect ophthalmoscopy, pre-treatment IOP measurements (recorded on

the Day 1 electronic case report form [eCRF] and dated accordingly), and any new concomitant medications.

Randomization will be stratified for the factors below:

- Baseline BCVA ETDRS letter score assessed on Day 1 (categories: ≤ 38 letters;
 > 38 to <64; ≥ 64).
- IVT anti-VEGF and/or periocular/IVT corticosteroids treatment naïve participants vs. previously treated participants (Note: treatment naïve and previously treated participants as defined in Section 5.2).

Randomization will be used to obtain an approximate equal allocation ratio between the different arms within each stratum. All participants will be randomized in a 1:1 ratio to one of the two arms. Limits will be placed on the number of treatment naïve and previously treated participants to ensure the planned distribution of participants in these two populations, i.e. per treatment arm approximately n=70 to 75 for treatment naïve and approximately n=35 to 40 for previously treated participants.

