8.2.6.3 Safety Finger Count Vision

In the study eye, a post-administration optic nerve head perfusion will be assessed for each participant immediately after IVT administration of study treatment or SoC (maximum within 15 minutes after treatment administration) by using testing finger count vision, hand motion, or light perception, as appropriate.

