8.3.6 Non-serious Adverse Events of Special Interest (immediately reportable to Roche)

Non-serious AEs of special interest are required to be reported by the Investigator to the Sponsor immediately (i.e., no more than 24 hours after learning of the event; see Appendix 2 for reporting instructions).

AEs of special interest (AESIs) for this study include the following:

- Cases of an elevated ALT or AST in combination with either an elevated bilirubin or clinical jaundice (as defined in Section 6 of Appendix 3).
- Suspected transmission of an infectious agent by the study treatment, as defined below:

Any organism, virus, or infectious particle (e.g., prion protein transmitting transmissible spongiform encephalopathy), pathogenic or non-pathogenic, is considered an infectious agent. A transmission of an infectious agent may be suspected from clinical symptoms or laboratory findings that indicate an infection in a participant exposed to a medicinal product. This term applies only when a contamination of the study treatment is suspected.

8.3.7 Sight-threatening Adverse Events (immediately reportable to Roche)

Sight-threatening AEs are defined in Appendix 8.

Sight-threatening AEs, regardless if considered serious or non-serious, are required to be reported by the Investigator to the Sponsor immediately (i.e., no more than 24 hours after learning of the event; see Appendix 2 for reporting instructions).

The follow-up actions for sight-threatening AEs are defined in Section 8.9.5.

8.3.8 Disease-Related Events and/or Disease-Related Outcomes Not Qualifying as Adverse Events or Serious Adverse Events

Not applicable.

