Appendix 8 Sight-Threatening Adverse Events

An adverse event is considered to be sight-threatening if it meets one or more of the following criteria:

- It causes a decrease of ≥30 letters in best corrected visual acuity (compared with the last assessment of VA prior to the most recent treatment) lasting more than 1 hour.
- It requires surgical intervention (i.e., conventional surgery, vitreous tap, or biopsy with intravitreal injection of anti-infectives, or laser or retinal cryopexy with gas) to prevent permanent loss of sight.
- It is associated with severe intraocular inflammation (i.e., 4+anterior chamber cell/flare or 4+vitritis; see grading scales for assessment in Appendix 6
- In the opinion of the Investigator, it may require medical intervention to prevent permanent loss of sight.

Signature Page for Protocol - BP43464 - IL-6 MAB - v3 - Global/Core - Published System identifier: RIM-CLIN-484021

Approval Task	
	Company Signatory
	23-Apr-2023 16:49:14 GMT+0000

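### The 30-letter criterion for a sight-threatening adverse event cannot be met by an eye scoring below 30 letters before treatment, although study eyes may enter from 19 letters

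*Protocol*

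**What the plan says.** Protocol Appendix 8 lists four criteria, any one of which makes an adverse event sight-threatening. The first is "It causes a decrease of ≥30 letters in best corrected visual acuity", with the fall measured as "compared with the last assessment of VA prior to the most recent treatment" and required to last more than 1 hour. The other three carry no letter threshold: surgery needed to prevent permanent loss of sight; severe inflammation (4+ anterior chamber cell or flare, or 4+ vitritis); and an investigator's opinion that medical treatment may be needed to prevent permanent loss.

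Section 5.1, criterion 7, admits study eyes "with BCVA letter score of 73 to 19 letters" at screening. Low-vision eyes are planned for: Section 6.3.1 stratifies randomization on "Baseline BCVA ETDRS letter score assessed on Day 1 (categories: ≤ 38 letters", followed by two higher categories. For the fellow eye, exclusion criterion 31 in Section 5.2 rules out 23 letters or fewer, so 24 or more is allowed.

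Two things follow from the label. Section 8.3.7 states: "Sight-threatening AEs, regardless if considered serious or non-serious, are required to be reported by the Investigator to the Sponsor immediately", which means within 24 hours. Section 8.9.5 recommends a safety blood sample and ophthalmological assessments with imaging when the event is potentially linked to the investigational product.

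**The concern.** The letter criterion is the only one of the four that works without a judgment about treatment or a grading of inflammation. If a score is already below 30, there are not 30 letters to lose, and Appendix 8 offers no substitute such as a fall to an off-chart level. The criterion therefore cannot operate in the eligible eyes with the least vision. What is at stake is how a rare, severe event is classified and worked up in a study of an investigational intravitreal antibody. The efficacy analysis is not involved.

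**Working it through.** The 30-letter threshold is stated without a derivation, so there is no plan figure to reproduce. The check is whether the threshold can be reached from each admissible score.

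**Inputs**
- Threshold: 30 letters (Appendix 8).
- Reference: last acuity before the most recent treatment (Appendix 8).
- Study-eye entry range: 19 to 73 letters inclusive (Section 5.1, criterion 7).
- Fellow-eye lower limit: 24 letters (Section 5.2, criterion 31).
- Scale floor: 0 letters. This is an assumption. The documents do not state it, but a count of letters read cannot be negative.

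**Formula:** largest possible loss = last pre-treatment score − floor. The criterion is reachable only if this is at least 30.

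| Last pre-treatment score | Largest possible loss | Criterion reachable? |
|---|---|---|
| 19 | 19 − 0 = 19 | No |
| 24 | 24 − 0 = 24 | No |
| 29 | 29 − 0 = 29 | No |
| 30 | 30 − 0 = 30 | Only if every letter is lost |
| 38 | 38 − 0 = 38 | Yes |

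**Counts of score values (not of patients)**
- Admissible entry scores: 73 − 19 + 1 = 55. Unreachable: 29 − 19 + 1 = 11. Share: 11/55 = 20%.
- Admissible entry scores of 38 or less: 38 − 19 + 1 = 20. Unreachable: 11. Share: 11/20 = 55%.
- Fellow eye, 24 to 29 letters: 29 − 24 + 1 = 6 score values with the same gap.

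**Sensitivity to the floor.** If the lowest recordable score were 1 or 4, the unreachable range would extend to 30 or 33. A higher floor only widens the gap.

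**Moving reference.** The reference is updated before each treatment. An eye that enters below 30 and improves to 30 or more comes within the rule. An eye that enters at 30 or more and falls below 30 leaves it.

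**The other routes.** Take a complete, non-inflammatory vascular loss that the investigator judges untreatable, once in an eye at 60 letters and once in an eye at 25.

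| Route | Eye at 60 letters | Eye at 25 letters |
|---|---|---|
| Letter criterion | Met if the loss lasts more than 1 hour (loss of 60) | Cannot be met (loss of at most 25) |
| Surgery | Not met | Not met |
| 4+ inflammation | Not met | Not met |
| Opinion that treatment may prevent permanent loss | Not met | Not met |
| SAE (Appendix 2, Section 2) | Open | Open |

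In this case the two eyes differ only in the first row. If surgery is needed, inflammation reaches 4+, or treatment might help, both eyes receive the label.

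**The case against.** The strongest reply is that little is lost in practice, and much of it stands.

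- **Other criteria.** One of four is enough, and the opinion criterion sets a low bar. A reader might infer that total loss of vision in an eye at 25 letters can never be called sight-threatening. The documents do not support that; only the letter criterion is closed.
- **24-hour reporting.** SAEs carry the same deadline whatever the relationship to treatment (Appendix 2, Sections 3.1 and 5). The SAE definition includes persistent or significant disability and important medical events. It would therefore be wrong to say that such losses escape expedited reporting. The SAE route still differs: it needs persistent or significant disability or a medical judgment, where the letter criterion needs a loss lasting more than 1 hour.
- **Work-up.** Section 8.9.5 only recommends its assessments, restricts them to events potentially linked to the product, and also applies them to any intraocular inflammation. Section 8.2.6 allows extra ophthalmological assessments at discretion, and Appendix 2, Section 4, requires further evaluation as medically indicated. What is lost is the specific recommendation; SAE status alone does not bring it back.
- **Counting.** A reader might infer that severe vision loss is under-counted in the lowest stratum. That is not shown. In the legible text, neither protocol Section 9.3.3 nor SAP Section 4.6.2 tabulates a sight-threatening class. The SAP does tabulate ocular adverse events and SAEs, and lists retinal vascular occlusive disease separately.
- **Size.** The 20% and 55% count score values. No baseline distribution is given. Assuming a normal distribution truncated to 19 to 73, mean/SD pairs of 60/11, 55/13, 52/14 and 50/15 put 0.3%, 2.4%, 4.9% and 7.4% of eyes below 30 letters. That runs from 0.003 × 180 = 0.5 to 0.074 × 230 = 17 participants at baseline. A spread of about 25-fold (7.4/0.3) is not an estimate. It also describes eyes at risk, of which only those with a catastrophic loss missing all three other criteria matter.

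**Conclusion.** The point holds in limited form. With a scale floor of 0, which is the one assumption, the letter criterion in Appendix 8 cannot be met from a pre-treatment score below 30, yet the protocol admits study eyes from 19 letters and fellow eyes from 24. For those eyes the label depends on surgery, 4+ inflammation or investigator opinion. The remaining gap is a complete loss meeting none of these. It would miss the automatic label and the Section 8.9.5 recommendation, while SAE reporting and ocular adverse event tabulation remain available.

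The number of such events is small and cannot be estimated from the documents. The primary endpoint, sample size and SAP tables are unaffected, and the legible list of mandatory discontinuation events in Section 7.1 does not use the letter criterion. This is a gap in a safety reporting definition, worth closing because the change is small.

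**What to change.** Reconcile the letter criterion in Appendix 8 with the 19-letter entry limit. Add an alternative for eyes whose last pre-treatment score is below 30 letters, for example loss of all measurable letters or a fall to an off-chart level. The exact wording is for the sponsor, consistent with how its acuity manual records off-chart vision.

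Keep the 1-hour condition, and state that persistence must be confirmed by a repeat acuity check when such an event is suspected. The existing post-injection test, done "by using testing finger count vision, hand motion, or light perception, as appropriate", cannot serve: Section 8.2.6.3 places it within 15 minutes of administration and in the study eye only.

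The cost is a short addition to Appendix 8 with matching eCRF guidance, a few more immediate reports, and an occasional unscheduled repeat acuity check. No new scheduled assessment and no SAP change are needed.

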Official Title: A Phase II, Multicenter, Randomized, Double Masked, Active

Comparator-Controlled Study to Investigate the Efficacy, Safety, Tolerability, Pharmacokinetics, and Pharmacodynamics of RO7200220 in Combination With Ranibizumab Administered

Intravitreally in Patients With Diabetic Macular Edema

NCT Number: NCT05151744

Document Date: Statistical Analysis Plan Version 3: 21-May-2024

STATISTICAL ANALYSIS PLAN (SAP)

TITLE: A PHASE II, MULTICENTER, RANDOMIZED,

DOUBLE MASKED, ACTIVE COMPARATOR-CONTROLLED STUDY TO INVESTIGATE THE

EFFICACY, SAFETY, TOLERABILITY,

PHARMACOKINETICS, AND

PHARMACODYNAMICS OF RO7200220 IN

COMBINATION WITH RANIBIZUMAB ADMINISTERED INTRAVITREALLY IN PATIENTS WITH DIABETIC MACULAR

EDEMA

PROTOCOL NUMBER: BP43464

SAP VERSION: 3

EUDRACT NUMBER: 2021-004390-31

IND NUMBER: 125644

TEST PRODUCT: RO7200220 in combination with ranibizumab

SPONSOR: F. Hoffmann-La Roche Ltd

PLAN PREPARED BY:

DATE FINAL: See electronic signature and date stamp

STATISTICAL ANALYSIS PLAN, VERSION 3: RATIONAL

The Statistical Analysis Plan has been amended to reflect changes in the primary estimand and sensitivity analyses.

This

original definition of the primary estimand is moved to a sensitivity analysis in this new Statistical Analysis Plan version and the primary estimand intercurrent events are redefined with definitions which are more restrictive.

Section 4.4.1 Primary Efficacy Estimand

The definition of the intercurrent events are modified.

Section 4.4.1.2 Sensitivity Analysis

An additional sensitivity analysis is added where the primary estimand is defined as in Statistical Analysis Plan versions 1 and 2.

This is an F. Hoffmann-La Roche Ltd document that contains confidential information. Nothing herein is to be disclosed without written consent from F. Hoffmann-La Roche Ltd.

TABLE OF CONTENTS

1.	BACKGROU	ND	7
2.	STUDY DES	IGN	7
	2.1	Protocol Synopsis	7
	2.2	Determination of Sample Size	7
	2.3	Analysis Timing	8
3.	STUDY CON	IDUCT	8
	3.1	Randomization	8
	3.2	Independent Review Facility	9
	3.3	Data Monitoring	9
	3.3.1	Safety IMC meetings	10
	3.3.2	Efficacy IMC meetings	10
	3.3.3 monitoring	Communication plan for unmasked data 10	
4.	STATISTICA	L METHODS	11
	4.1	Analysis Populations	11
	4.2	Analysis of Study Conduct	13
	4.3	Analysis of Treatment Group Comparability	14
	4.4	Efficacy Analysis	14
	4.4.1	Primary Efficacy Estimand	15
	4.4.1.1	Analysis Methods	17
	4.4.1.2	Sensitivity Analysis	17

VEGF vascular endothelial growth factor

1. BACKGROUND

This proof-of-concept Phase II study seeks
Besides efficacy
(primary endpoint), it will further assess its safety, tolerability, pharmacokinetics (PK),
and pharmacodynamics (PD).
The analyses specified in this document supersede the analysis plan described in the

2. STUDY DESIGN

study protocols.

2.1 PROTOCOL SYNOPSIS

The Protocol Synopsis is in Appendix 1. For additional details, see the Schedule of Assessments in Appendix 2.

2.2 DETERMINATION OF SAMPLE SIZE

Approximately 60 treatment-naïve participants will be enrolled in each arm to ensure that
approximately 55 treatment-naïve participants will be evaluable at Week 48 for the
primary efficacy outcome.

Additionally, approximately 30 previously treated participants will be enrolled in each arm to ensure that approximately 25 previously treated participants will be evaluable at Week 48 for the primary efficacy outcome. This number is considered sufficient to assess the difference between the treatment and control arms in the change in CST from baseline to Week 48.

Approximately 180 participants will be enrolled in this study.

Not all participants recruited will be evaluable at Week 48 because protocol version 1 stipulated participants would have their last treatment visit at Week 20, compared to Week 44 in Protocol Version 2 (signed July 2022). At the time of implementation of Protocol Version 2 (October 2022), some participants had already entered the off-treatment observation stage of the trial under Protocol Version 1.

2.3 ANALYSIS TIMING

The primary analysis will be performed when all participants have either completed the study treatment phase until Week 48 or have discontinued from the study prior to Week 48, and all data collected prior to the primary LPLV are in the database and have been cleaned and verified. At the time of the primary analysis, the study will be ongoing as participants continue in the off-treatment observation phase after completing the treatment phase. Results of the primary analyses, summarized by treatment group, may be reported to the public before completion of the study. Participants and masked study site personnel will remain masked to individual treatment assignment until the study is completed, the database is locked, and the study analyses are final.

The final analysis will be performed when all participants either have completed the study until Week 72 or have discontinued early from the study, all data from the enrollment phase are in the database and have been cleaned and verified.

3. STUDY CONDUCT

3.1 RANDOMIZATION

Using a stratified permuted block randomization method, participants are randomized in a 1:1 ratio so that approximately 90 participants are randomized to each of the two arms

- Arm A: 1.0 mg RO7200220 IVT Q4W and ranibizumab 0.5 mg IVT Q4W
- Arm B: 0.5 mg ranibizumab IVT Q4W (active-control arm).

Randomization is stratified by baseline BCVA Early Treatment Diabetic Retinopathy Study (ETDRS) letter score, as assessed on Day 1 (categories: ≤ 38 letters; > 38 to <64; ≥ 64) and prior IVT anti-VEGF/corticosteroid therapy (IVT anti-VEGF and/or periocular/IVT corticosteroids treatment-naïve participants vs. previously treated participants). Randomization will be performed through an IxRS (Interactive Voice/Web Response System) and the first study treatment will be administered on the same day as randomization (i.e., at the Day 1 visit).

Randomization will be used to obtain an approximate equal allocation ratio between the different arms within each stratum. All participants will be randomized in a 1:1 ratio to one of the two arms. Limits will be placed on the number of treatment-naïve and previously treated participants to ensure the planned distribution of participants in these two populations, i.e. per treatment arm approximately n=60 for treatment-naïve and approximately n=30 for previously treated participants.

After randomization and at each visit with study treatment administration (i.e., Day 1 until Week 44), the IxRS will assign the appropriate study treatment kit to be used.

3.2 INDEPENDENT REVIEW FACILITY

All ocular images are obtained by trained and certified site personnel at the study sites and forwarded to CRCs (Central Reading Centers), for independent analysis and storage. As part of the screening process, the CRCs evaluate ultra-wide field [UWF] color fundus photographs ([UWF]-FPs), ultra-wide field fundus fluorescein angiographies ([UWF]-FFAs), and SD-OCT images to provide an objective, masked assessment of participant eligibility. During the study treatment period, the CRCs provide a masked evaluation of all ocular images including (UWF)-FP, (UWF)-FFA, SD-OCT or, and optional OCT angiography (OCT-A). The data resulting from this masked review of ocular images are forwarded to the Sponsor.

